--	---

	
 • Section 4.6 Prior and Concomitant Medications: added medications of interest, aligned with study RSV3001, to assess the use of these medications of special interest and their potential impact on the PRESORS assessments. • Section 5.2.3 Analysis Method: added sensitivity analysis excluding nasal swab samples identified as: 
 ○ Ribonuclease P (RNase P [housekeeping gene]): result = Target Not Detected AND ○ RSV A: result = Target Not Detected AND ○ RSV B: result = Target Not Detected • Section 5.3.1.1 RSV RNA Viral Load, 5.3.1.2 PRESORS, 5.3.1.3 Other Clinical Course Parameters 
 ○ Added definitions, derivations and tabulation of missing data PRESORS ObsRO/ClinRO. ○ Added tabulation of number of caregivers/investigators. • Section 5.3.1.3.2 Hospitalized Subjects only: 
 ○ Revised time (hours) to end of supplementation (oxygen and/or feeding/hydration) to include up to 72h from first hospital discharge specification. Definition was revised, based on previous IAs, to ensure accurate derivation of resolution per subject and not one confounded by continued use of supplementation. ○ Clarified that normalization of vital signs (HR and RR) is based on investigator evaluation only. ○ Added definition, derivations and tabulation of re-hospitalization. • Section 5.3.2 Endpoint-specific Analysis Methods: 
 ○ Streamlined time to event analysis by removing all references to COX proportional analysis model as the same information can be obtained from the AFT analyses. ○ Updated AFT model to exclude baseline \log_{10} RSV RNA viral load as covariate for clinical course endpoints. ○ Expanded methodology for association between key endpoints and baseline indicators of interest ○ Revised methodology for comparing proportions accounting for the randomization stratification factors. • Section 5.4: Exploratory Endpoints: the exploratory efficacy endpoints listed in Section 5.4 have additionally been included, based on previous IAs with new information becoming available during the course of the study. These additional exploratory efficacy endpoints support decision-making for further development of JNJ-53718678 and interactions with health authorities. • Section 5.6 Decision Rules at Interim Analyses: the calculation of conditional power for the change from baseline in key RSV symptoms at Day 8 was corrected to account for the correlation between Z_{TV}, the test statistic to test the null

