Situation	Censoring										
Last ObsRO assessment indicates resolution of RSV symptoms but insufficient recordings to meet the time to resolution requirement (24h)	Censored at first record of resolution from the last series of recordings of resolution of RSV symptoms (concepts)										
Last ObsRO assessment does not indicate resolution of RSV symptoms	
After the last observation, censored at 08:00 on the same day if the last observation was a morning diary entry (from 00:00 until 01:59)
 
After the last observation, censored at 20:00 on the same day if the last observation was a morning diary entry (from 02:00 until 13:59)
 
Censored at 8:00 the next day if the last entry was an evening diary entry (from 14:00 until 23:59)
										
Death (without previous resolution)	Censored at date/time of death										
Missing information to determine resolution of symptoms (concepts) because of (re-)hospitalization (without previous resolution)	Censored at date/time of (re-)hospitalization										
Time (hours) to resolution of RSV [summary parameters] [time to event]	
For the 4 summary parameters:
 
 • Key RSV symptoms • Respiratory symptoms • General illness behavior • Overall RSV symptoms 
Time (hours) from first dose of study drug until the date/time of first observed resolution of all individual RSV concepts (symptoms)
										

Table 17: Parameters based on PRESORS ObsRO

Measurement	Formula
	
comprising the relevant summary parameter (refer to Attachment 2 for concepts comprising each RSV summary parameter).
 
In case not all RSV concepts, comprising a summary parameter, are resolved, data will be censored. Similar rules as for time to resolution of each ObsRO individual symptom (concept) will be applied.
 
time to event (hours) = (date/time of event or censoring – date/time of first dose of study drug)/3600, rounded to one decimal

Status of RSV symptoms at each timepoint [categorical]	
Each assessment of ‘Keeping in mind all the symptoms you observed [recall period], overall how would you rate the child’s RSV symptoms now?’ will be assigned to one of the 6 categories below:
 
  None  Very mild  Mild  Moderate  Severe  Very severe

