The aforementioned will be presented overall by treatment group and by the subgroups as defined in Section 2.4, for summary parameters, key RSV symptoms and overall RSV symptoms only.

For time to resolution of summary parameters, key RSV symptoms and overall RSV symptoms (ObsRO), sensitivity analyses will be performed considering 4 different imputation methods:

- Method 1: from first resolution (score 0 or 1) after last unresolved value onwards, impute missing data as resolved.

- Method 2: impute all missing values as unresolved (score >1).
- Method 3: impute all missing values in-between resolved observations (score 0 or 1) as resolved.
- Method 4: impute all missing values as unresolved (score >1), except when in-between resolved values where resolved is imputed.

These sensitivity analyses will be provided from IA#3 onwards.

In addition, for the summary parameters, key RSV symptoms and overall RSV symptoms, difference in median time (hours) to resolution (event) between each active treatment group as compared to placebo will be investigated using the AFT model with log-logistic distribution. The model will include class variables treatment group with placebo as reference and randomization stratification factors (derived) and baseline summary parameter score. Summary will include parameter estimates and associated standard error, covariance matrix of parameter estimates, estimated accelerated failure time ratio (as compared to placebo) and both 80% and 95% 2-sided confidence intervals.

The aforementioned will be presented overall by treatment group and by the subgroups as defined in Section 2.4.

Parameter estimates and associated variance matrix resulting from AFT model, will be used in a generalized MCP-Mod approach to test dose-response, at 1-sided alpha level=0.10. The aforementioned MCP-Mod will be presented overall by treatment group only.

Graphical presentation will include:

- Overlay of survival curves with Kaplan-Meier survival function and AFT on one plot
- Forest plot of accelerated failure time ratios and resulting confidence intervals for subgroups of interest as defined in Section 2.4 including the relevant subgroup variable as covariate in the model with subgroup*treatment group interaction.

Status of RSV Symptoms, Status of Health, Status of Improvement of RSV Symptoms, Status of Return to Pre-RSV Disease Health (ObsRO)

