5.4. Exploratory Endpoints

Section 2.1.2 Endpoints of protocol, Amendment #6 (dated 01 December 2020), includes a detailed overview of efficacy and other endpoints (primary, secondary and exploratory) as planned per protocol. The exploratory efficacy endpoints listed below are additionally included, based on previous IAs with new information becoming available during the course of the study. These additional exploratory efficacy endpoints support decision-making for further development of JNJ-53718678 and interactions with health authorities.

Unless otherwise specified, the additional exploratory efficacy endpoints listed below, **will be analyzed and presented primarily for those subjects with symptom onset ≤ 3 days before randomization.**

Parent/Caregiver PRESORS ObsRO

- In hospitalized subjects (Cohort 1): RSV Recovery Scale (RRS): Day 1 to Day 8
- Time (hours) to resolution of RSV symptoms (concepts) and four summary parameters (ObsRO): ‘supplemental-free’ definition (*at least 24h oxygen- and hydration/feeding supplementation free*)

Note: aforementioned time (hours) to resolution (‘supplemental free’ definition) for both RSV concepts and summary parameters, developed during the course of the study based on new information available, is considered the primary definition of time (hours) to resolution for subsequent analyses. The addition of ‘at least 24h supplementation free’ requirement is to ensure that evaluation of time (hours) to resolution is an accurate reflection of the actual subject’s resolution status rather than a time (hours) confounded by possible continued use of supplementation.

- Potential association between the time (hours) to resolution of key- and overall RSV summary parameters (ObsRO [‘supplemental-free’ definition]) and covariates and/or baseline indicators of interest
- Time (hours) to resolution of key- and overall RSV summary parameters from hospital discharge (ObsRO): ‘supplemental-free’ definition (*at least 24h oxygen- and hydration/feeding supplementation free*)
- Resolved status per timepoint:
 - Day 1 to Day 8
 - BEFORE (last PRESORS ObsRO BEFORE)/AFTER (first PRESORS ObsRO AFTER) hospital discharge
- Sustained resolution of key- and overall RSV summary parameters
- AUC from immediately prior to first dose of study drug (baseline) through Day X (AUC_{Day X}), Day 8 (AUC_{Day 8}) and Day 10 (AUC_{Day 10}): key RSV symptoms

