Time (hours) to resolution of RSV [summary]	Four summary parameters: 
 • Key RSV symptoms • Respiratory symptoms

Measurement	Formula

parameter]: 24h supplementation free definition [time to event]
	
 General illness behavior Overall RSV symptoms 
In the subset of hospitalized subjects (Cohort 1), time (hours) from first dose of study drug until the date/time of first observed resolution of all individual RSV concepts comprising the relevant summary parameters (refer to Attachment 2 for concepts comprising each RSV summary parameter). Where resolution occurs when ALL criteria, noted below, are met:
 
 All individual RSV concepts comprising relevant summary parameter are scored as 0 (none) or 1 (mild) for approximately 24h AND At least 24h oxygen supplementation free AND At least 24h hydration/feeding supplementation free) 
If caregiver is completing the ObsRO as expected per protocol, the approximate 24h summary score resolution can be defined with the considerations as detailed in Section 5.3.1.2.1.
 
In case not all RSV concepts, comprising a summary parameter, are resolved, data will be censored. Similar rules as for time to resolution of each ObsRO individual symptom (concept) will be applied as described in Section 5.3.1.2.1, such that:
 
time to event (hours) = (date/time of event or censoring – date/time of first dose of study drug)/3600, rounded to one decimal

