- PRESORS ObsRO summary parameters: key RSV symptoms and overall RSV symptoms:
 - Time (hours) to resolution (ObsRO): *24h supplementation free definition*
 - Change from Baseline in PRESORS ObsRO: key RSV symptoms and overall RSV symptoms at Day X, Day 8 and Day 10
 - Where Day X is defined as the day when at least 50% of Cohort 1 subjects, across all treatment groups, have been discharged from hospital
- RSV-related complications (Yes vs No): modified definition

As new information becomes available, additional clinical course endpoints may be identified and explored utilizing the above methodology to ascertain possible relationships.

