5.6. Decision Rules at Interim Analyses

During IAs, the primary viral load endpoint and 3 below-mentioned key clinical course endpoints are considered. Minimum acceptable value and target value for these key clinical course endpoints are defined in [Table 23](#):

Table 23: MAV and TV

Endpoint	Minimum Acceptable Value (MAV)	Target Value (TV)
Time to resolution of key RSV symptoms (ObsRO)	No difference (MAV = 0)	1 day (24 hours) reduction (TV = -1)
Change from baseline (CFB) in summary parameter: key RSV symptoms (ObsRO) at Day 8	No difference (MAV = 1)	20% larger change from baseline, where the change from baseline represents a reduction in score (TV = 1.2*)
Incidence of RSV-related Complication	No difference (MAV = 0)	10% absolute reduction in rate (TV = -0.1)

* This represents a 20% increase in the magnitude of the CFB and not in the summary parameter score itself (i.e. if the CFB in the Placebo treatment group is -1.0, then the target CFB for the active treatment group would be -1.2)

Note that the viral load endpoint will be evaluated on a combined dataset of both cohorts for each interim analysis, except for IA#1 where only Cohort 1 data are available. Clinical course endpoints will be evaluated in the community cohort only for IA#3 and IA#4.

For IA#3 and IA#4 analyses, in case of severe imbalance between ≤ 3 days and > 3 days since symptom onset and where there are more subjects in the > 3 to ≤ 5 days stratum than in the ≤ 3 days stratum (i.e. $> 55\%$ of subjects in the > 3 to ≤ 5 days stratum), a second analysis will be conducted considering 50% of subjects randomized in each stratum (symptom onset ≤ 3 days and symptom onset vs > 3 to ≤ 5 days) in each cohort separately. Chronological order of randomization (date and time) per stratum will be followed when defining the balanced dataset. In case there are inconsistencies in the results between the complete and the balanced analysis, no decision on altering the study (i.e. stopping for futility or enriching) will be taken and the study will proceed as planned and collect more data. In the case that a balanced analysis has been carried out (as described above), the sample size re-estimation at IA#3 will be performed on the balanced dataset only.

The IDMC will provide recommendations to the SC according to the below guidance:

Interim Analysis 1

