- The time to resolution of key RSV symptoms will be analyzed using an accelerated failure time (AFT) model, using the log-logistic distribution as described in Section 5.3.2.2. However, the term for baseline \log_{10} viral load will be retained whether or not it is significant at the 10% significance level. The median time to resolution for the placebo group (T_p) in days will be estimated based upon this model and the TV that corresponds to a 1-day reduction for the high dose group will be calculated as a log relative reduction (i.e. as $\log[(T_p-1)/T_p]$). The MAV of no difference corresponds to a log relative reduction of $\log(T_p/T_p) = 0$. The 1-sided p-values for the tests to compare the difference between the high dose and placebo groups versus the TV and MAV will be derived using normal approximations for appropriate contrasts, Z_{TV} and Z_{MAV} .

Change from baseline in key RSV symptoms at Day 8

- The change from baseline in key RSV symptoms at Day 8 will be analyzed using a restricted maximum likelihood repeated measures approach as described in Section

5.3.2.2. The adjusted mean reduction from baseline for the placebo group will be estimated based upon this model (\bar{x}_P) and the TV that corresponds to a 20% larger change from baseline for the high dose group (i.e. $1.2\bar{x}_P$) will be calculated. The MAV corresponds to a difference in the change from baseline of 0 (i.e. $1.0\bar{x}_P$). The 1-sided p-values for the tests to compare the difference between the high dose and placebo groups versus the TV and MAV will be derived using normal approximations for appropriate contrasts, Z_{TV} and Z_{MAV} .

Incidence of RSV-related complications

- The 1-sided p-values to compare the proportion of subjects with at least one RSV-related complication between the high dose and placebo groups versus the MAV and TV will be derived using a normal approximation to the binomial distribution; where:

$$\hat{p}_1 - \hat{p}_2 \sim N \left(p_1 - p_2, \frac{p_1(1-p_1)}{n_1} + \frac{p_2(1-p_2)}{n_2} \right)$$

The TV of an absolute reduction in rate of 10% corresponds to a difference in the proportion of subjects with at least one RSV-related complication in high dose versus placebo of -0.1. The MAV corresponds to a difference in the proportions of 0.

For each of the three clinical course endpoints, the conditional probability for the Stop decision for the situation without/with enrichment and for each assumed total sample size will be calculated as:

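### IA#3 conditional power for time to resolution of key RSV symptoms keeps a viral-load covariate that the referenced model lacks, and the decision rules do not name the resolution definition they use

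*SAP*

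**What the plan says.** **Model.** Section 5.6 sets out how the IA#3 p-values against the target value (TV) and the minimum acceptable value (MAV) are obtained for each key clinical endpoint. For time to resolution of key RSV symptoms it uses the log-logistic AFT of Section 5.3.2.2, with one qualification: the baseline log10 viral-load term "will be retained whether or not it is significant at the 10% significance level". Section 5.3.2.2 lists the covariates in full: "The model will include class variables treatment group with placebo as reference and randomization stratification factors (derived) and baseline summary parameter score".

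**Definition.** Table 17 (Section 5.3.1.2.1) defines resolution of a summary parameter as all its component concepts scored 0 or 1 for about 24 hours. It sets no supplementation condition and no cohort restriction. Section 5.4 adds a variant that also requires at least 24 hours free of oxygen and of feeding/hydration supplementation, and says this variant "is considered the primary definition of time (hours) to resolution for subsequent analyses". The derivation in Table 22 (Section 5.4.1) begins "In the subset of hospitalized subjects (Cohort 1), time (hours) from first dose of study drug until the date/time of first observed resolution". Section 5.5 nevertheless lists the variant among the Cohort 2 endpoints.

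**Use in decisions.** Section 5.6 states: "Clinical course endpoints will be evaluated in the community cohort only for IA#3 and IA#4". Table 23 and the Bonferroni-Holm text in Section 5.2.3.2 give the endpoint by name only.

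**The concern.** Section 5.6 overrides a term and a selection rule that the model it points to does not contain. A programmer can add viral load for IA#3 only, or ignore the sentence as a leftover, and the two choices give different results. IA#4 has no model text of its own, and the final MCP-Mod test takes its estimates from the Section 5.3.2.2 AFT. If the sentence is followed, IA#3 therefore forecasts an analysis that will be run differently.

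Three IA#3 outputs depend on these calculations: the enrichment rule (at least 2 of 4 endpoints with conditional power below 50%), the Go, Stop and inconclusive probabilities, and through the last of these the Cohort 2 sample-size re-estimation.

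The definition gap is a second and smaller matter. One sentence in Section 5.4 can be read as changing the endpoint for everything that follows, although the variant has no derivation in the cohort used for the decisions.

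**Working it through.** **1. The two model statements side by side**

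| | Section 5.3.2.2 | Section 5.6 (IA#3) |
|---|---|---|
| Distribution | log-logistic | same, by reference |
| Covariates | treatment, derived strata, baseline summary score | the same, plus baseline log10 viral load |
| 10% selection step | none | assumed to exist, then overridden |

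The amendment history points to a leftover: Amendment 3 records excluding baseline log10 "RSV RNA viral load as covariate for clinical course endpoints". That is only a sign of intent. The contradiction stands in the current text without it.

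**2. The SAP's own figure for this kind of endpoint, used to choose a scale**

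Section 1.4 gives 48 per arm, a 3-day placebo median, a 1-day reduction and a scale parameter of 1/0.65, for a 95% probability of an effect in the right direction. For an uncensored log-logistic AFT, SE = σ·√(3·(1/48 + 1/48)).
- σ = 0.65: SE = 0.230, log(3/2)/SE = 1.76, probability 96.1%. This agrees with 95% to within 2 points.
- σ = 1/0.65: probability 77.2%. This does not agree.

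So σ = 0.65 is used below.

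**3. Conditional power for Go at IA#4**

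Inputs: n1 = 75 (Section 5.2.3.2), n_Primary = 225, so w1 = 1/3. The IA#4 total is 150 (Section 5.6), so n2 = 75. No enrichment is assumed.
- CRV_MAV = (1.2816 − √(1/3)·Z)/√(2/3) = 1.570 − 0.707·Z
- μ_MAV = √(75/75)·Z = Z
- MAV side: CP_Go = Φ(1.707·Z − 1.570)
- 50% is reached at Z = 1.570/1.707 = 0.92
- Slope there: 0.399 × 1.707 = 0.68 per unit of Z. An assumed shift of 0.2 gives 0.2 × 0.68 ≈ 0.14, about 14 points.

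The formula takes the smaller of the TV and MAV sides. The MAV side is the smaller when |TV|/SE < 2 × 1.570/1.707 = 1.84. With 25 per arm, SE = 0.65·√(6/25) = 0.318. For T_p = 3 days, |TV|/SE = 0.405/0.318 = 1.27, and it is lower for longer medians. The MAV side therefore binds.

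**4. The target also depends on the fitted model**

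The TV is log[(T_p − 1)/T_p], with T_p the placebo median estimated from the same AFT. The SAP gives no Cohort 2 median. Over an assumed range:

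| T_p (days) | 3 | 4 | 5 | 6 | 7 | 8 |
|---|---|---|---|---|---|---|
| TV | −0.405 | −0.288 | −0.223 | −0.182 | −0.154 | −0.134 |

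**5. How far adding or dropping viral load can move Z**

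Simulation, all inputs assumed: 25 per arm, σ = 0.65, T_p = 5 days, 1-day effect in both dose groups, viral-load SD 1.5 log10, no censoring, no other covariates, 300 runs per row.

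| Viral-load coefficient per log10 | SD of change in Z | Runs in which the 80% CI against the MAV changes verdict |
|---|---|---|
| 0 | 0.14 | 5% |
| 0.1 | 0.17 | 4% |
| 0.2 | 0.30 | 7% |
| 0.3 | 0.44 | 14% |

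A shift of 0.2 in Z is thus within the ordinary range.

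**6. Tracing the definition**

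Section 5.6 points to Section 5.3.2.2, which opens by referring to Section 5.3.1.2.1, where Table 17 stands. That route gives a definition usable in Cohort 2. The Section 5.4 note points to Table 22, which covers Cohort 1 only. The rule in Section 5.3.1.2.1 that decision rules use modified definitions settles concept scoring. It does not choose between these two.

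**The case against.** Several points on the other side are sound.

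- The word that introduces the viral-load sentence could mark a deliberate addition. Even so, the sentence presupposes a selection step found nowhere in Section 5.3.2.2, so the two sections still need reconciling.
- The Section 5.6 model text covers the IA#3 p-values only. A reader might infer that IA#4 has two competing models. It does not: with no text of its own, it falls back on Section 5.3.2.2.
- A reader might infer that the covariate breaks an equality between the IA#3 p-values and the stage-one p-values of the final combination test. No such equality exists. The quantity written p_Full in Section 5.6 is the viral-load p-value. The clinical p-values at IA#3 are high-dose-versus-placebo contrasts, whereas Section 5.2.3.2 combines MCP-Mod p-values. They differ by design.
- A reader might infer from Section 5.4 and Table 22 that the decision endpoint is undefined in Cohort 2. The cross-references lead to Table 17, which has no cohort restriction. Elsewhere, when a changed definition is meant to drive decisions (modified PRESORS scoring, modified complications), the SAP says so. The Section 5.4 note has no such clause and sits among exploratory endpoints.
- One endpoint crossing 50% does not by itself trigger enrichment. Two of four are needed, and the IDMC then only considers it.
- The choice of definition touches few Cohort 2 subjects: 1 to 3 per arm if 5% to 10% of about 25 are admitted (assumed). Table 17 already censors where hospitalization leaves the information missing.

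These points narrow the finding. They do not remove the model contradiction, or the silence of Table 23 and the Holm text.

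**Conclusion.** The model statement in Section 5.6 is wrong as written and should be fixed. If followed, the IA#3 Go and Stop probabilities for one of the three key clinical endpoints come from a model that IA#4 and the final analysis do not fit. Both the Z statistics and the TV can then move. Near the 50% threshold the effect is about 14 points of conditional power per 0.2 in Z. That rests on 75 Cohort 2 subjects at IA#3, no enrichment, and an assumed shift. In the simulation, the verdict of the 80% interval against the MAV changed in about 4% to 14% of trials, under assumed inputs.

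The definition issue is an ambiguity and does not leave the endpoint missing. The decision rules lead to Table 17, but only through two cross-references and against a general sentence in Section 5.4. The real gap is narrower: Section 5.5 asks for a Cohort 2 endpoint that has no Cohort 2 derivation.

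**What to change.** 1. In Section 5.6, delete the sentence on the viral-load term. Use the Section 5.3.2.2 AFT (treatment, derived strata, baseline key-symptom score) at IA#3, IA#4 and the final analysis.
2. In Table 23 and Section 5.2.3.2, state that the Table 17 definition with modified scoring drives the decision rules and the Holm test in Cohort 2.
3. Limit the Section 5.4 note on the primary definition to the exploratory analyses it covers.
4. For Cohort 2, either write a derivation of the supplementation-free definition, for use in Section 5.5 and as a sensitivity analysis, or remove it from the Cohort 2 list there.

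Moving the supplementation-free definition into Table 23 and the Holm test is not advised. Section 5.4 says it was developed during the study and that these endpoints were added on the basis of earlier interim analyses, so using it in the error-controlled test would raise a larger question than it settles.

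Items 1 to 3 are SAP wording only. Item 4 is also wording if the endpoint is removed. If a derivation is written, first confirm that supplementation start and stop times are recorded for Cohort 2, because Table 20 specifies those parameters for hospitalized subjects.
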